2.6 Hypothesis

The hypothesis to be tested is that 1.5g calcium supplementation a day to low calcium intake nulliparous pregnant women reduces the risk of pre-eclampsia as compared with the placebo group.

3 Study design

The study will be a multicentre randomized, placebo-controlled, double-blind trial. The calcium supplement will be 1500 mg/day given as carbonate. This will be a pragmatic trial in which all nulliparous women presenting for antenatal care at any time before 20th week of gestation regardless of their gynaecological history or other obstetric characteristics will be eligible for the trial.

3.1 Settings

The trial will be conducted in antenatal clinics in developing countries serving a population of women with low calcium intake. The collaborating centres will be from the following countries that have expressed an interest to participate in the trial: Argentina, Colombia, Egypt, India, Peru, South Africa and Vietnam. These centres, which have experience in conducting trials, have been contacted and feasibility studies have been completed. These centres also have experience in detailed follow-up of large numbers of women. The study population in these centres should have a considerable proportion of women starting antenatal care before 20 weeks of pregnancy, an already existing routine antenatal care system and capacity to monitor all deliveries. Moreover base-line calcium intake from the

populations served by these centres (similar to the population to be recruited) will be completed before enrolment starts.

3.1.1 Routine antenatal and postnatal care

The study will not alter or interfere with any treatment or care given routinely to women in the antenatal care clinics or delivery institutions selected for the trial. Routine measures should include at least:

1. Attendance at ANC clinics starting before 20 weeks of pregnancy (up to 19 weeks and 6 days). The frequency and content of the visits will follow the standard practice of the clinic but at least one clinical visit will be carried out every four weeks to all enrolled women.
2. Monitoring standardized blood pressure measurement and routine urine screening for proteinuria at each antenatal care visit.
3. Assessment of birth weight and gestational age at delivery or shortly afterwards.

3.2 Intervention: calcium supplements

The women will be randomized to receive either a calcium supplement or a placebo from the time of enrolment, until delivery or initiation of any magnesium sulphate treatment, or the suspicion of urolithiasis. Women starting antenatal care before the twentieth week will be randomized at the first visit. Most of the women will therefore be supplemented for approximately five to six months. The diagnosis of pre-eclampsia or hypertension is not a reason for discontinuation of treatment.

The choice of calcium carbonate as the supplement was made because it is the cheapest of all other calcium supplements, making it more feasible for programme implementation in the case that the trial demonstrates its effectiveness and because all published studies and an ongoing trial in the Gambia have used this salt. Furthermore, several studies have demonstrated the absorption of calcium carbonate to be higher in comparison with other calcium salts.

There will be three chewable tablets containing 500 mg elemental calcium to be taken every day. Women will be instructed to chew tablets at meals, but at least 3 hours away from any iron supplements^{30 31 32}. The control group will receive three tablets a day of identical characteristics, colour and taste as the intervention tablet prepared and packed by the same pharmaceutical manufacturer.

All women will be encouraged not to take any additional calcium supplements. For those women who need analgesics, acetaminophen, and for those needing antacids, a non-calcium antacid will be recommended.

The dose 1500 mg/day, lower than the 2000 mg/day used in previous trials was selected for the following reasons:

- a) The study populations have an intake level (median < 600 mg/day) that will be raised to a level above the RDA of 1200 mg with 1500 mg/day supplementation.

b) This level of calcium intake is more likely to be achievable from dietary sources alone. In this way, if the trial shows beneficial results from supplementation, the populations will not have to depend solely on supplementation by tablets.

c) Compliance is likely to be higher with three tablets. Problems with compliance have been reported in previous trials where women expressed problems with taking 4 large tablets every day. Furthermore, the tablets that will be used in this trial will be chewable and it is anticipated that compliance will be less of a problem in this trial. Insufficient compliance does not constitute a reason for excluding a patient from the trial.

3.3 Participants

3.3.1 Eligibility criteria

Pregnant women attending antenatal care in the participating centres will be eligible if the following criteria are met:

1. Gestational age <20 weeks
2. Nulliparous
3. Willing and able to give consent. (Informed consent for minors will be obtained following country specific age limits)

Randomization will be conducted during the first ANC visit before 20 weeks of gestation. It was decided to include all nulliparous women regardless of their gynaecological history or early pregnancy complications (such as threatened abortion or hyperemesis gravidarum) to cover a high-risk group most readily identifiable. Although there are other risk factors such as positive family history and pre-eclampsia in a previous pregnancy, the screening process to identify these cases is likely to be cumbersome and will be difficult to implement given the diverse populations included in the trial.

3.3.2 Exclusion criteria

Women will be excluded under the following conditions:

- History of urolithiasis or symptoms suggestive of urolithiasis or any renal disease such as haematuria, flank pain, etc.
- Parathyroid disease.
- Blood pressure ≥ 140 mmHg systolic or ≥ 90 mmHg diastolic, receiving treatment or had history of hypertension.
- Taking diuretics or any digoxin treatment.
- Plan to deliver in a health facility outside the study area or at home.
- Taking phenytoin or tetracyclines.

3.4 Outcome variables

Outcome variables are classified as primary or secondary. The primary outcomes of the study are selected on the bases of the following: they can be affected by the intervention, represent an important clinical outcome, are recorded routinely by treatment blinded observer and occur frequently to provide sufficient statistical power. The primary maternal outcome of the trial is pre-eclampsia. The definitions for trial endpoints are described in detail in appendix 7.

Hypertension is defined as blood pressure greater than or equal to 140 mmHg systolic and/or 90 mmHg diastolic occurring in two occasions at least four hours to a week apart after the 20th week of pregnancy. Diastolic blood pressure will be measured at 5th Korotkoff sound, which is the disappearance of the sounds. Proteinuria is defined if protein in urine is ≥ 300 mg in 24 hours urine specimen or corresponding level of 2+ or more on dipstick.

Preeclampsia is defined as hypertension associated with proteinuria. Severe pre-eclampsia is defined as 160 mmHg systolic and/or 110 mmHg diastolic or greater on two occasions at least 4 hours apart or a single BP reading of 160 mmHg and/or 110 mmHg or greater if it required treatment with an antihypertensive and at least 2+ proteinuria.

For women directly admitted to a hospital without being referred from an antenatal clinic with a diagnosis of pre-eclampsia, the highest recorded blood pressure measurement will be extracted from medical records and diagnosis of high blood pressure will be based on it.

Maternal secondary outcomes are: Early onset pre-eclampsia (pre-eclampsia starting before 32 weeks of gestation), pregnancy induced hypertension (PIH), eclampsia and placental abruption.

The primary neonatal outcome is pre-term birth (<37 weeks of gestation). Neonatal secondary outcomes are low birth weight (birth weight <2500 grams), spontaneous pre-term delivery and medically indicated pre-term delivery, admission to newborn intensive care unit for more than 2 days, fetal and neonatal mortality, and perinatal mortality.

A random sample of medical records of delivered patients with and without pre-eclampsia will be photocopied and reviewed by a team of independent investigators to evaluate the agreements between study definitions and clinical diagnoses.

3.5 Methods

3.5.1 Sample size and power considerations

The total minimum sample size was determined to be 8500 women, with half allocated to receive calcium supplements and the other half to receive placebo tablets. This sample size is sufficient to obtain 80% power to detect a 30% reduction in the rate of pre-eclampsia in the calcium group (2.8%), as compared with the placebo group rate of 4%. This rate in the placebo group is based on data obtained from one of the populations considered for the study, with HRP/RHR/WHO supported population based data collection system. This rate is at the lower end of the range from other candidate centres and gives the sample size calculation a conservative approach. An even more conservative estimation is a reduction in the rate of pre-eclampsia from 3.5% in the placebo to 2.45% in the calcium group, which requires a total of 9000 women. A total of 4500 women will be sufficient to show a reduction from 4% to 2.40% or a RR of 0.60. This latter sample size will be used as the milestone for the first interim analysis.

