10.1.3	Data processing and system preparation	20
10.1.4	Statistical issues	20
10.2	Conduct of the trial	20
10.2.1	Coordination activities	20
10.2.2	Administrative.....	21
11	Links with other projects.....	21
12	Main problems anticipated	21
13	Expected outcomes of the study	22
13.1	Clinical.....	22
13.2	Public health	22
14	Dissemination.....	22
15	Authorship for publications	22
16	TRIAL COMMITTEES	24
16.1	Local investigators and institutions	24
16.2	Steering Committee	24
16.3	Data and Safety Monitoring Committee	24
17	APPENDICES	25
	APPENDIX 1: SYSTEMATIC REVIEW OF CALCIUM SUPPLEMENTATION.....	26
	APPENDIX 2: DUMMY TABLES FOR ANALYSES	29
	APPENDIX 3: FLOW CHART OF WOMEN APPROACHED DURING THE TRIAL	32
	APPENDIX 4: SAMPLE CONSENT FORM	33
	APPENDIX 5: TIMELINE FOR THE TRIAL	34
	APPENDIX 6: CONSORT STATEMENT REQUIREMENTS	35
	APPENDIX 7: ENDPOINT DEFINITIONS.....	36
18	References	37

1 Summary

Hypertensive disorders of pregnancy (HDP) affect approximately 10% of all pregnancies. The aetiology and pathophysiology of HDP are still largely unknown and an ideal prevention and treatment strategy does not exist. Although there has been progress in perinatal survival, largely due to developments in care of small babies, HDP continue to be major contributors to maternal and perinatal morbidity and mortality, especially in developing countries. The systematic review of randomized controlled trials of calcium supplementation provides promising evidence that calcium supplementation may be effective in preventing HDP in women with low calcium intake. It is important to obtain a reliable, definitive answer to this question for both clinical and programmatic reasons.

The World Health Organization and its collaborating institutions in developing countries propose a double-blind randomized controlled trial (RCT) to evaluate the impact of calcium supplementation (1.5 g/d) started before the twentieth week of pregnancy to nulliparous women with low calcium intake, on the incidence of pre-eclampsia. The proposed trial will enrol approximately 8500 women in seven countries over a period of 18 months. The primary outcomes are the incidence of pre-eclampsia (hypertension and proteinuria) for women and preterm birth for newborns. The sample size calculation is based on a reduction in the rate of pre-eclampsia from 4% in the placebo group to 2.8% in the calcium-supplemented group (30% reduction).

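### Section 3.5.1: the three sample sizes do not share one basis, and the 9000 given for the 3.5% scenario is the one out of line

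*Protocol*

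**What the plan says.** Section 3.5.1 of the protocol makes three numerical statements about the primary maternal outcome, pre-eclampsia, with 1:1 allocation.

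- Main scenario, 4% on placebo and 2.8% on calcium: "The total minimum sample size was determined to be 8500 women, with half allocated to receive calcium supplements". The section adds: "This sample size is sufficient to obtain 80% power to detect a 30% reduction in the rate of pre-eclampsia".
- More cautious scenario: "a reduction in the rate of pre-eclampsia from 3.5% in the placebo to 2.45% in the calcium group", "which requires a total of 9000 women".
- Interim milestone: "A total of 4500 women will be sufficient to show a reduction from 4% to 2.40% or a RR of 0.60".

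Power is stated once, for the main scenario. Section 3.5.1 gives no alpha, sidedness, formula or loss allowance. Section 8.6 gives 0.05 as the level for the final analysis, and states a two-sided test for the interim look only. Section 8.2 says that losing patients will reduce outcome detection, but gives no rate.

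**The concern.** Lowering the control rate from 4% to 3.5% while holding the relative reduction at 30% should raise the required number by roughly 15%. The protocol's totals rise by 6%. If 8500 is the minimum for the first scenario, 9000 looks too small for the second. If 9000 is right for the second, 8500 is more than the minimum for the first.

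The 3.5% line is the protocol's own sensitivity case. Someone judging how well the trial stands up to a low event rate would read from it that a fall to 3.5% costs 500 more women. The section also leaves unclear whether its totals are women randomised or women analysed, so the power of the planned 8500 at 3.5% cannot be read from it.

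**Working it through.** **Inputs.** Rates and totals are from section 3.5.1 and allocation is 1:1. Alpha of 0.05 is from section 8.6. A two-sided final test is assumed, because section 8.6 states it only for the interim. Power is 80%. Loss is not stated, so 0%, 5%, 10% and 15% are shown as assumptions.

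**Formula** (pooled two-proportion test, per arm, with p̄ the mean of p1 and p2):

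n = [1.96·√(2p̄(1−p̄)) + 0.8416·√(p1(1−p1) + p2(1−p2))]² / (p1 − p2)²

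**Step 1: try to reproduce the stated totals.**

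- 4% v 2.8%: p̄ = 0.034; n = [1.96 × 0.25630 + 0.8416 × 0.25616]² / 0.012² ≈ 3579 per arm, total 7158.
- 3.5% v 2.45%: p̄ = 0.02975; n = [1.96 × 0.24027 + 0.8416 × 0.24016]² / 0.0105² ≈ 4109 per arm, total 8217.
- 4% v 2.4%: p̄ = 0.032; n = [1.96 × 0.24890 + 0.8416 × 0.24864]² / 0.016² ≈ 1898 per arm, total 3796.

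| Scenario | Stated | Needed, uncorrected | Stated/needed | Needed, continuity-corrected | Stated/needed |
|---|---|---|---|---|---|
| 4% v 2.8% | 8500 | 7158 | 1.187 | 7488 | 1.135 |
| 3.5% v 2.45% | 9000 | 8217 | 1.095 | 8594 | 1.047 |
| 4% v 2.4% | 4500 | 3796 | 1.185 | 4043 | 1.113 |

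None of the stated totals is reproduced without an allowance. The first and third carry nearly the same margin; the second does not. A search over alpha, sidedness, power, continuity correction and loss from 0% to 30% found no single basis that gives all three totals within 3%.

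**Step 2: compare the two 30%-reduction scenarios directly.** The required ratio is 8217 / 7158 = 1.148. It stays at 1.148 for alpha 0.01, 0.05 and 0.10, for power 80% and 90%, and with or without continuity correction. A common loss rate cancels from the ratio. The stated ratio is 9000 / 8500 = 1.059. So this mismatch does not depend on the unstated alpha, power or loss.

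**Step 3: find the like-for-like figure for 3.5%.** With no loss it is 8217, or 8594 with continuity correction. Scaled to the basis implied by 8500, it is 8500 × 8217 / 7158 ≈ 9760.

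**Step 4: compute power over a range of assumed loss** (uncorrected formula, with N(1 − loss) analysed):

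| Assumed loss | 8500 at 4% v 2.8% | 9000 at 3.5% v 2.45% | 8500 at 3.5% v 2.45% |
|---|---|---|---|
| 0% | 86% | 83% | 81% |
| 5% | 85% | 82% | 79% |
| 10% | 83% | 79% | 77% |
| 15% | 80% | 77% | 75% |

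With no loss and a continuity correction, the first two entries in the 0% row become 85% and 82%.

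**The case against.** The best defence rests on the wording. The totals 8500 and 4500 are described as sufficient, and only 9000 is described as required. All three statements can then be true together. With 8.5% loss and the uncorrected formula, the needs are 7823, 8981 and 4149; with 4.5% loss and continuity correction they are 7841, 8999 and 4233. Either way 9000 is the requirement at 3.5%, and the other two totals are ample. This shows that neither 8500 nor 4500 is false as a lower bound. It does not reconcile the section, because 8500 is also called the minimum, and on those bases the minimum is below 7900.

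Three stronger readings are tempting, and the protocol does not support them.

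- A reader might infer that the 80% for 8500 is an error because full analysis gives 86%. A design with 86% power is still sufficient for 80%.
- A reader might infer that 9000 is short by several hundred women. That depends on a loss of about 15%, which is back-calculated by treating 8500 as an exact minimum and is stated nowhere. On the uncorrected formula, 9000 keeps 80% power up to a loss of 1 − 8217/9000 = 8.7%. The opposite inference, that 8500 already covers 3.5% if nobody is lost, holds uncorrected (8217) but not with continuity correction (8594).
- A reader might infer that the sponsor would extend enrolment to 9000 if events ran low. No section provides for that. The 3.5% case is offered as a comparison, and the planned enrolment is 8500.

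It is also fair to say that nothing the protocol sets out to do depends on 9000. That limits the consequence but leaves the inconsistency in place.

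**Conclusion.** The point holds as an internal inconsistency in the primary-outcome sample-size section. The two 30%-reduction totals should differ by a factor of about 1.15 and differ by 1.06. Since 8500 and 4500 agree with each other, 9000 is the outlier. This rests only on the printed rates and totals and on reading 8500 as the minimum the section calls it.

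The power figures rest on more: two-sided alpha of 0.05, the uncorrected formula, and assumed loss. On that footing, over 0% to 15% loss, 8500 has 86% to 80% power at 4%, and 81% to 75% at 3.5%. The inconsistency does not make the main target underpowered. The defect is that the sensitivity case understates the cost of a lower event rate, and that the basis of all three totals is unstated.

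**What to change.** Rewrite section 3.5.1 on a single basis. State alpha, sidedness, formula, power and the sponsor's own loss allowance once, and say whether the totals are women randomised or women analysed. Recompute all three totals from that basis. Replace 9000 with the like-for-like figure, or delete it. That figure is about 8220 uncorrected or 8590 continuity-corrected with no loss, and about 9760 if scaled to the basis implied by 8500. Add the power that 8500 gives at 3.5% v 2.45%.

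The 15% loss should not be written in as if it had been the design assumption; the sponsor has to supply its own figure. The cost is a few sentences, with no change to enrolment.

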3.5.2 Randomization

Simple randomization will be conducted independently for each study site by the HRP/RHR statistical unit at WHO headquarters and provided to the pharmaceutical manufacturer.

The random allocation sequence will be generated using computer-generated random numbers. Randomization will be to the two arms of the trial and stratified by country. Blocking with randomly varying groups of 6-8 will be used to restrict randomization within the strata (country) (SAS Software, Copyright© 1989, 1994 SAS Institute, Inc., N.C., USA).

Random allocation technique consists of allocating consecutively numbered treatment boxes for each woman, including in each box seven independent bottles, each of them with tablets for four weeks of treatment. Each bottle contains 100 tablets. Therefore each subject will have seven bottles with the same randomization number. Treatment boxes will be kept at the clinic. Bottles will be provided consecutively as needed every month after randomization. When the woman comes for antenatal care, she will return the used bottle from the previous month and will be given the next month's bottle from her box. She will return the bottle after 4 weeks, regardless of whether she finished the tablets or not. Each bottle is numbered from 1 to 7 within the box and should be used sequentially.

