8.5 Analysis plan

An analysis plan has been finalised before recruitment starts. A draft layout of the proposed analysis plan is presented in Appendix 2 in dummy tables.

Principal analyses will be on an intention-to-treat principle with comparisons made between calcium and placebo for primary and secondary outcomes. Stratification will be made for

time gestational age of entry into the trial by each woman and by baseline calcium intake level of populations served by the hospitals. These hospitals will be classified as serving a population of very low (< 200mg), low (200-400mg), or medium (400-599mg) calcium intake before initiation of the trial. An exploratory analysis will be conducted for the hypothesis that the effect will be larger among women who started treatment before 16th week of pregnancy and among populations with the lowest baseline calcium intake.

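### Scheduled supply is 28 weeks per woman, but entry has no lower gestational limit and treatment runs to delivery, so some early entrants run out before delivery

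*Protocol*

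**What the plan says.** **Supply.** Protocol section 3.5.2 allocates one numbered box per woman, "including in each box seven independent bottles, each of them with tablets for four weeks of treatment". It adds: "Each bottle contains 100 tablets". All seven bottles carry her randomization number, and neither a second box nor any resupply is described.

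**Exchange.** Section 3.5.2 gives two intervals. One sentence reads "Bottles will be provided consecutively as needed every month after randomization"; another reads "She will return the bottle after 4 weeks, regardless of whether she finished the tablets or not". Section 5.1 mixes them in the same way: visits are monthly, and each new bottle is for the following four weeks.

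**Daily intake.** Section 3.2: "There will be three chewable tablets containing 500 mg elemental calcium to be taken every day".

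**Entry.** Section 3 opens the trial to "all nulliparous women presenting for antenatal care at any time before 20th week of gestation". Section 3.3.1 requires a gestational age under 20 weeks and gives no minimum. Randomization takes place at the first visit.

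**Treatment period.** Section 3.2 runs treatment "from the time of enrolment, until delivery or initiation of any magnesium sulphate treatment", or until urolithiasis is suspected. Section 7 restricts discontinuation to refusal, parenteral magnesium sulphate and suspected urolithiasis. Section 3.2 also expects about five to six months of supplementation for most women.

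**Analysis.** Section 8.5 plans an exploratory analysis of the hypothesis that "the effect will be larger among women who started treatment before 16th week of pregnancy".

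**The concern.** Each rule is clear on its own, but together they cannot all be followed for the earliest women the protocol admits. A woman entered early enough uses up her seven bottles before she delivers. The protocol then has her still on treatment with no bottle to give her, and no listed reason for stopping.

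The timing matters. Section 2.1 says pre-eclampsia is usually diagnosed late in pregnancy, which is when these women would be without tablets. Both arms run out alike, so the comparison is not confounded. Only the calcium arm loses active treatment, however, so any error is dilution toward no effect. All the affected women belong to the stratum in which section 8.5 expects the larger effect.

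**Working it through.** **Inputs from the protocol:** 7 bottles per box, 100 tablets per bottle and four weeks per bottle (3.5.2); 3 tablets a day (3.2); entry before 20 weeks with no minimum (3, 3.3.1).

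**Assumption:** delivery at 40 weeks, with a range of 37 to 42. The protocol gives only the preterm cut-off of 37 weeks.

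**Step 1: the plan's own schedule.** 7 × 4 = 28 weeks.

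**Step 2: tablets.** Four weeks need 28 × 3 = 84 tablets, so a 100-tablet bottle has 16 spare. The box holds 7 × 100 = 700 tablets, and 700 / 3 = 233.3 days = 33.3 weeks. The 28-week limit therefore comes from the return rule, not from the box contents.

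**Step 3: calendar-month exchange.** A month is 365.25 / 12 = 30.44 days and needs 91.3 tablets, which one bottle can supply. Cover is 7 × 30.44 / 7 = 30.4 weeks.

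**Step 4: earliest entry fully covered** = delivery week − weeks of cover.

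| Reading of the exchange rule | Cover (weeks) | Delivery at 37 | Delivery at 40 | Delivery at 42 |
|---|---|---|---|---|
| Strict four-week exchange | 28.0 | 9.0 | 12.0 | 14.0 |
| Calendar-month exchange | 30.4 | 6.6 | 9.6 | 11.6 |
| Every tablet used | 33.3 | 3.7 | 6.7 | 8.7 |

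On every reading the threshold is below 16 weeks, so all affected women are in the early-start stratum.

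**Step 5: when supply ends** = entry week + cover.

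| Entry week | Strict | Calendar month | Every tablet |
|---|---|---|---|
| 6 | 34.0 | 36.4 | 39.3 |
| 8 | 36.0 | 38.4 | 41.3 |
| 10 | 38.0 | 40.4 | 43.3 |

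With delivery at 40 weeks, the strict reading leaves 6, 4 and 2 weeks uncovered for entry at 6, 8 and 10 weeks. The monthly reading leaves 3.6, 1.6 and 0 weeks. Using every tablet leaves 0.7, 0 and 0 weeks.

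**Step 6: the protocol's expectation for most women.** Five to six months is 21.7 to 26.1 weeks. With delivery at 40 weeks this means entry between 40 − 26.1 = 13.9 and 40 − 21.7 = 18.3 weeks. Seven bottles suffice for these women on every reading.

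**The case against.** The strongest reply is that the problem is narrow. Four parts of it stand.

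- **The box is not short by tablet count for most entrants.** A reader might infer from the seven four-week bottles that the box physically holds 28 weeks of tablets. It holds 33.3 weeks. What limits use is the return of unfinished bottles, and the monthly wording loosens even that. The fate of the last bottle's 16 spare tablets (16 / 3 = 5.3 days) is also unsettled, since no further bottle replaces it.
- **Not every woman entered before 12 weeks runs out.** That figure assumes strict exchange and delivery at 40 weeks. A woman entered at 11 weeks who delivers at 39 is fully covered.
- **Most women are covered** by the protocol's own expectation of five to six months.
- **The stratum analysis is exploratory.** Early entrants who run out have still had 28 scheduled weeks, more than women entered at 14 to 19 weeks receive by 40 weeks (26 to 21).

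Two stronger readings are tempting but unsupported. One is a material loss of power. The protocol gives neither the share of women entering this early nor the share of their cases arising after supply ends, nor how quickly any effect wears off. Any power figure would rest on invented inputs, and under mild ones the loss is close to nil. The other is that the compliance index in Appendix 2, Table 6 is distorted. The protocol does not define its ideal number of tablets, and that definition can properly be left to the analysis plan.

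The reply does not remove the contradiction. Each reading of the exchange rule leaves some permitted entrants without supply before a 40-week delivery, and the protocol does not say which reading applies.

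**Conclusion.** The point holds as an inconsistency between supply and treatment period for a minority of early entrants. Followed literally, the rules supply 28 weeks. With delivery at 40 weeks, women entered before 12 weeks run out first (9 to 14 weeks for delivery at 37 to 42). The threshold falls to 9.6 weeks under calendar-month exchange and to 6.7 weeks if every tablet is used.

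The thresholds rest on the assumed delivery week and on which exchange rule applies. The number of women affected cannot be derived from the protocol. The consequence is dilution toward the null, probably small in the whole trial and confined to the early-start stratum. The sample size calculation is not called into question. The point is worth correcting because the contradiction is plain and the gap falls late in pregnancy.

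**What to change.** Before the boxes are packed, reconcile two sets of statements:

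1. the entry window and treatment period in sections 3, 3.2, 3.3.1 and 7;
2. the box contents and the exchange and return rule in sections 3.5.2 and 5.1, including whether the interval is four weeks or a month.

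The aim is that scheduled supply and stated treatment period agree for every permitted entry. Which statement gives way is for the trial team; this review takes no position on it.

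The cost is low: some unused bottles or tablets, or a small change of wording.
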